## 3. Study Procedures:

- Diagnosis, Medical Review, and Prescription of Therapy (Screening, Day -3 to Day -1):
  - Subject will provide electronic informed consent via the EDC portal.
  - Medical Information
    - a. Study staff will review prior and concomitant medications, including over-the-counter medications and supplements.
    - b. Investigator will review the Subject's records during the screening process, looking at inclusion/exclusion criteria, gathering data on vital signs, EKG recordings, and oxygen saturation. These values will be used to compare to values obtained throughout the study. If any contraindication to participation is found, the study drugs will not be provided and the subject will be deemed a screen failure.
  - Diagnosis of COVID-19 will be confirmed
    - a. May be based on PCR testing results, rapid antigen testing results, or clinical presentation at screening as assessed by the Principal Investigator including symptoms such as:
      - Fever
      - Cough
      - Anosmia
  - Subject will be provided a daily diary for recording symptoms.
  - Subject will be randomized into Arm 1 or Arm 2
  - Prescription of treatment drugs
    - a. Arm 1: Medications will be prescribed for Quintuple Therapy
      - Hydroxychloroquine 200MG BID for 10 days, Azithromycin 500mg on day 1, 250mg day 2-5, Vitamin C 3000mg for 10 days, then 1500mg for 20 days, Vitamin D 3000IU for 10 days, then 1500IU for 20 days, and zinc 50mg for 10 days, then 25mg for 20 days.
    - b. Arm 2: Placebos and supplements will be provided (to ensure nutritional parity)
      - Placebo for Hydroxychloroquine BID for 10 days, Placebo for Azithromycin to be taken 2 the on Day 1, then 1 on Days 2-5, Vitamin C 3000mg for 10 days, then 1500mg for 20 days, Vitamin D 3000IU for 10 days, then 1500IU for 20 days, and zinc 50mg for 10 days, then 25mg for 20 days.
    - c. Drugs shall be taken first thing in the morning as soon as the patient has eaten. Vitamins will be taken with lunch and dinner, and then the evening dose of drugs will be right before bed.
  - Monitoring equipment provided
    - a. Home EKG recording device

- b. Pulse Oximeter
    - c. Thermometer
    - d. Urine Pregnancy test if applicable
  - Subject will be isolated as an outpatient
    - a. All CDC recommendations regarding self-quarantine must be followed
- Treatment Period
  - Day 1 following positive test (isolation)
    - a. Subject will be video called to ensure they have all study materials and go over:
      - Use of home health equipment
        - Subject will take baseline measurements at this time and record it in the diary
      - Diary and how to transmit its contents
      - Medication dosing
    - b. Subject will take pregnancy test if applicable
    - c. Subject will use provided equipment to measure vital signs
      - EKG
      - Oxygen Saturation
      - Temperature
    - d. Subject will take prescribed regimen

Drug	AM Dose	PM Dose
Hydroxychloroquine (or Placebo)	200mg	200mg
Azithromycin (or Placebo)	500mg	---
Vitamin C	1500mg	1500mg
Vitamin D	1500IU	1500IU
Zinc	25mg	25mg

- Hydroxychloroquine and azithromycin will be taken early in the morning with breakfast and right before bed. Vitamins and Zinc will be taken with lunch and dinner
  - Day 2
    - a. Subject will complete AM and PM diaries
    - b. Subject will use provided equipment to measure vital signs
      - EKG
      - Oxygen saturation
      - Temperature
    - c. Subject will take prescribed regimen

Drug	AM Dose	PM Dose
Hydroxychloroquine (or Placebo)	200mg	200mg
Azithromycin (or Placebo)	250mg	---
Vitamin C	1500mg	1500mg
Vitamin D	1500IU	1500IU
Zinc	25mg	25mg

- Day 3
    - a. Subject will be called
      - Ask if they are experiencing any difficulties with swab collection
      - Ask about AE/SAE
      - Update list of prior and concomitant medications
      - Ask about symptom resolution or progression

- Instruct how to collect nasal or oropharyngeal swabs
  - Subject will collect first nasal or oropharyngeal swab
- Answer any questions the Subject may have
- b. Subject will complete AM/PM diaries
- c. Subject will use provided equipment to collect vital signs
  - EKG
  - Oxygen saturation
  - Temperature
- d. Subject will take prescribed regimen

Drug	AM Dose	PM Dose
Hydroxychloroquine (or Placebo)	200mg	200mg
Azithromycin (or Placebo)	250mg	---
Vitamin C	1500mg	1500mg
Vitamin D	1500IU	1500IU
Zinc	25mg	25mg

○ Day 4

- a. Subject will complete AM/PM diaries
- b. Subject will use provided equipment to collect vital signs
  - EKG
  - Oxygen saturation
  - Temperature
- c. Subject will take prescribed regimen

Drug	AM Dose	PM Dose
Hydroxychloroquine (or Placebo)	200mg	200mg
Azithromycin (or Placebo)	250mg	---
Vitamin C	1500mg	1500mg
Vitamin D	1500IU	1500IU
Zinc	25mg	25mg

○ Day 5

- a. Subject will complete AM/PM diaries
- b. Subject will be called
  - remind them to collect swab
  - Ask about AE/SAE
  - Update list of prior and concomitant medications
  - Answer any questions
- c. Subject will collect nasal or oropharyngeal swab
- d. Subject will use provided equipment to collect vital signs
  - EKG
  - Oxygen saturation
  - Temperature
- e. Subject will take prescribed regimen

Drug	AM Dose	PM Dose
Hydroxychloroquine (or Placebo)	200mg	200mg
Azithromycin (or Placebo)	250mg	---
Vitamin C	1500mg	1500mg
Vitamin D	1500IU	1500IU
Zinc	25mg	25mg

- Day 6
  - a. Subject will complete AM/PM diaries
  - b. Subject will use provided equipment to collect vital signs
    - EKG
    - Oxygen saturation
    - Temperature
  - c. Subject will take prescribed regimen

Drug	AM Dose	PM Dose
Hydroxychloroquine (or Placebo)	200mg	200mg
Vitamin C	1500mg	1500mg
Vitamin D	1500IU	1500IU
Zinc	25mg	25mg

- Day 7
  - a. Subject will be called
    - Ask about AE/SAE
    - Ask about symptom resolution or progression
    - Update list of prior and concomitant medications
    - Answer any questions the Subject may have
  - b. Subject will collect nasal or oropharyngeal swab
  - c. Subject will complete AM/PM diaries
  - d. Subject will use provided equipment to collect vital signs
    - EKG
    - Oxygen saturation
    - Temperature
  - e. Subject will take prescribed regimen

Hydroxychloroquine (or Placebo)	200mg	200mg
Vitamin C	1500mg	1500mg
Vitamin D	1500IU	1500IU
Zinc	25mg	25mg

- Day 8
  - a. Subject will complete AM/PM diaries
  - b. Subject will use provided equipment to collect vital signs
    - EKG
    - Oxygen saturation
    - Temperature
  - c. Subject will take prescribed regimen

Drug	AM Dose	PM Dose
Hydroxychloroquine (or Placebo)	200mg	200mg
Vitamin C	1500mg	1500mg
Vitamin D	1500IU	1500IU
Zinc	25mg	25mg

- Day 9
  - a. Subject will complete AM/PM diaries
  - b. Subject will use provided equipment to collect vital signs
    - EKG
    - Oxygen saturation
    - Temperature

- c. Subject will take prescribed regimen

Drug	AM Dose	PM Dose
Hydroxychloroquine (or Placebo)	200mg	200mg
Vitamin C	1500mg	1500mg
Vitamin D	1500IU	1500IU
Zinc	25mg	25mg

- o Day 10

- a. Subject will be called

- Remind them to decrease dosage of vitamins C, vitamin D, and zinc tomorrow
- Ask about AE/SAE
- Ask about symptom resolution or progression
- Update list of prior and concomitant medications
- Answer any questions the Subject may have

- b. Subject will complete AM/PM diaries

- c. Subject will use provided equipment to collect vital signs

- EKG
- Oxygen saturation
- Temperature

- d. Subject will take prescribed regimen

Drug	AM Dose	PM Dose
Hydroxychloroquine (or Placebo)	200mg	200mg
Vitamin C	1500mg	1500mg
Vitamin D	1500IU	1500IU
Zinc	25mg	25mg

- o Day 11-Day 13

- a. Subject will complete AM/PM diaries

- b. Subject will take prescribed regimen

Drug	AM Dose	PM Dose
Vitamin C	750mg	750mg
Vitamin D	750IU	750IU
Zinc	12.5mg	12.5mg

- o Day 14

- a. Subject will be called

- Remind them to collect nasal or oropharyngeal swab
- Ask about AE/SAE
- Symptom resolution or progression
- Answer any questions the Subject may have

- b. Subject will collect nasal or oropharyngeal swab

- c. Subject will complete AM/PM diaries

- d. Subject will take prescribed regimen

Drug	AM Dose	PM Dose
Vitamin C	750mg	750mg

Vitamin D	750IU	750IU
Zinc	12.5mg	12.5mg

- Day 15-30
  - a. Subject will complete AM/PM diaries
  - b. Subject will take prescribed regimen

Drug	AM Dose	PM Dose
Vitamin C	750mg	750mg
Vitamin D	750IU	750IU
Zinc	12.5mg	12.5mg

- Follow-Up Period (These visits can be conducted via videoconference or in person)
  - Month 1 (outpatient only AFTER negative test)
    - a. Vital signs (BP, HR, RR, oxygen saturation, temperature)
    - b. Assessment for AE and SAE
    - c. EKG (Optional)
    - d. Physical exam (Optional)
    - e. Blood draw for CBC/Complete metabolic panel/C-Reactive Protein/Blood hydroxychloroquine levels/SARS-CoV Antibody test (All optional)
      - Blood HQ levels will remain blinded from all but unblinded coordinator
    - f. Update list of prior and concomitant medications
    - g. Study team will collect nasal or oropharyngeal swab (If patient elects to refrain from this in-person visit they will collect this at home)
  - Month 2 (outpatient)
    - a. Vital signs (BP, HR, RR, oxygen saturation, temperature)
    - b. Assessment for AE and SAE
    - c. EKG (Optional)
    - d. Physical exam (Optional)
    - e. Blood draw for CBC/Complete metabolic panel/C-Reactive Protein (Optional)
    - f. Update list of prior and concomitant medications
  - Month 3 (outpatient)
    - a. Vital signs (BP, HR, RR, oxygen saturation, temperature)
    - b. Assessment for AE and SAE
    - c. EKG (Optional)
    - d. Physical exam (Optional)
    - e. Blood draw for CBC/Complete metabolic panel/C-Reactive Protein (Optional)
    - f. Update list of prior and concomitant medications
    - g. Study team will collect nasal or oropharyngeal swab (If patient elects to refrain from this in-person visit they will collect this at home)
    - h. Pregnancy test (if applicable)
- COVID-19 sample collection
  - Nasal swabs will be collected according to CDC protocol
    - a. Synthetic fiber swabs with plastic shafts
      - NP swabs will be collected by insertion of a swab into the nostril parallel to the palate. The swab will be left in place a few seconds to allow it to absorb secretions
    - b. Swabs will be immediately placed in sterile tubes with 2-3mL of viral transport media
    - c. The tubes will be placed in biohazard bags then boxes. The boxes will be sterilized and then collected by rapid carrier for delivery to the central lab.
  - Oropharyngeal swabs will be collected according to CDC protocol
    - a. Synthetic fiber swabs with plastic shafts
      - Swab will be inserted into the mouth and will touch the area near the tonsils five

times.

- b. Swabs will be immediately placed in sterile tubes with 2-3mL of viral transport media
  - c. The tubes will be placed in biohazard bags then boxes. The boxes will be sterilized and then collected by rapid carrier for delivery to the central lab.
- Hospitalization
    - Should Subject's symptoms worsen, they will be referred to their PCP for further evaluation and possible hospitalization

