**Duration of Subject Participation (Study Visits)**

Subjects will be given the opportunity once diagnosis has been made via RT-PCR testing to participate. They may be recruited through the ProgenaBiome website, through a questionnaire. They may also be recruited through [www.clinicaltrials.gov](http://www.clinicaltrials.gov). Subjects may be referred by healthcare facilities. Subjects may also self-refer as well. All potential Subjects will be called during the recruitment process for screening assessments. The first step of this will be to obtain informed consent electronically, via the EDC. We will attempt to connect with these Subjects via Zoom/telemedicine. The validity of the test used to diagnose will be verified through medical records. (The diagnosis will be made by the Subject's evaluating physician or evaluation testing center, as part of the standard of care when infection is suspected). Following successful screening, Subjects will be randomized into the Arm 1 (treatment) or Arm 2 (placebo). At this time the associated treatment regimen will be prescribed and shipped to the Subject's home, along with home health equipment (MoMe Kardia II, thermometer, pulse oximeter and pregnancy test). Subjects will take azithromycin for 5 days, and hydroxychloroquine for 10 days, along with vitamin C, vitamin D, and zinc. Starting at Day 11 Subjects will discontinue hydroxychloroquine and reduce the doses of vitamin C, vitamin D, and zinc. The vitamin C, D, and zinc will be taken an additional 20 days at the reduced dose. Subjects will use the home EKG to transmit heart function information to the Study Team to be read by a board-certified cardiologist prior to dosing. The EKG will then be used daily for 10 days and results transmitted to the study team. Subjects will use a home pulse oximeter to monitor oxygen saturation and photographically report these values to the study team via the EDC. Subjects will track their symptoms using a daily diary (provided). Subjects will collect nasal or oropharyngeal swabs on Days 3, 5, 7, 14, and Month 1 and Month 3 for RT-PCR testing. Once Subjects have tested negative following treatment with HAZDpaC, Subjects will present to the clinic at 1, 2, and 3 months post-treatment for viral testing via RT-PCR. Alternatively, these visits may be conducted via videoconference and the subjects may collect these samples at home. At these visits blood will be drawn, a physical exam performed, and vital signs measured (optional). At the month 3 visit a pregnancy test will be given if applicable. Should Subject remain symptomatic at 2 weeks, or return to a positive state at any time during the trial they will be referred to their PCP by a phone call directly from the PI to the PCP. If at any time during the treatment phase or subsequent follow up Subject expresses and demonstrates a worsening or persistence of symptoms, they will be cared for according to standard of care or referred to their primary care provider, according to patient preference. The PI will discuss the case directly with that primary care provider. Subjects will continue to be followed for the remainder of the trial, and documentation of any additional treatments and Subject outcomes will be collected.

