### Exclusion Criteria

1. Refusal to provide informed consent
2. Pregnant or breastfeeding women
3. Diarrhea prior to infection
4. Negative test for COVID-19 by RT-PCR or rapid antigen test at screening
5. Any comorbidities which, in the opinion of the investigator, constitute health risk for the subject
6. Any contraindications for treatment with hydroxychloroquine
  - a. Hypoglycemic
  - b. Known G6PD deficiency
  - c. Porphyria
  - d. Anemia
  - e. Neutropenia
  - f. Alcoholism
  - g. Myasthenia gravis
  - h. Skeletal muscle disorders
  - i. Maculopathy
  - j. Changes in visual field
  - k. Liver disease
  - l. Psoriasis
  - m. History of QT interval >500msec
  - n. History of torsades de pointes
7. Anemia from pyruvate kinase and G6PD deficiencies
8. Abnormal EKG with QT prolongation acquired or from birth
9. Allergies to 4-Aminoquinolines
10. History of jaundice or high fevers prior to developing COVID-19
11. Treatment with any of the medications listed in Appendix II
12. Treatment with any other drug not listed that affects the QT interval
13. Treatment with any anti-epileptics

ProgenaBiome, LLC Protocol PRG-044	21 July2020
Number of Subjects	
Subjects will be enrolled to ensure that at least 600 complete the study. It is anticipated that screening of 1200 Subjects will be required to achieve this.	
Specimen Requirements:	
NP swabs (synthetic swab on plastic shaft) placed into 2-3mL of viral transport media. 1 mL of blood in an EDTA and 2 mL of serum in two serum separator tubes spun down	
Study Duration	
Screening of 1200 Subjects and enrollment of 600 Subjects is expected to take 3 months	

Primary Study Objective	Study Endpoints
The rate of recovery from COVID-19 in Subjects using Quintuple Therapy	Number of days from COVID-19 diagnosis to recovery via RT-PCR
Reduction or Progression of Symptomatic Days	Reduction and/or progression of symptomatic days, reduction of symptom severity
Secondary Objectives	Study Endpoints
Assess the safety and Tolerability of Quintuple Therapy	Assess the symptom response to study therapy as measured by the survey in the EDC
	EKG response, oxygen saturation, and vital signs at baseline, 2 weeks, 1 month, and two months
	Assess Adverse Events and Serious Adverse Events due to Quintuple Therapy

- a. Adverse event monitoring will be conducted for 12 weeks
- b. Serious adverse event monitoring will be conducted for 12 weeks

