## 2. Trial Objectives

Primary Study Objective	Study Endpoints
The rate of recovery of mild or moderate COVID-19 in Subjects using Quintuple Therapy	Number of Days Recovery from COVID-19 diagnosis to Recover via RT-PCR
Secondary Objectives	Study Endpoints
Assess the safety of Quintuple Therapy	Assess the symptom response to study therapy as measured by the survey in the EDC
	EKG response, oxygen saturation, and vital signs at baseline, 2 weeks, 1 month, and two months
Assess Tolerability of Quintuple Therapy	Assess Adverse Events and Serious Adverse Events due to Quintuple Therapy

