## **6. Schedule of Events**

On next page

Assessment	Screening (Day -7 to Day 1)	Day 1	Day 2	Day 3	Day 4	Day 5	Day 6	Day 7	Day 8	Day 9	Day 10	Day 11	Day 12	Day 13	Day 14	Days 15-30	Month 1 (± 4 days)	Month 2 (± 4 days)	Month 3 (± 4 days)
Informed Consent & Demographics	X																		
Make list of prior and concomitant medications	X			X				X			X				X		X	X	X
Confirmation of COVID-19 diagnosis	X																		
Review of Medical Records	X																		
Prescription of Antimicrobials a	X																		
Provide home health equipment b	X																		
Pregnancy test c		X																	X
Call Subject at home d		X		X		X		X			X				X				
Vitals at home e		X	X	X	X	X	X	X	X	X	X								
Subject will complete AM/PM diary		X	X	X	X	X	X	X	X	X	X	X	X	X	X	X			
Hydroxychloroquine 200mg BID (or placebo)		X	X	X	X	X	X	X	X	X	X								
Azithromycin 500mg (2 tablets) once daily (or placebo)		X																	
Azithromycin 250mg (1 tablet) once daily (or placebo)			X	X	X	X													
Vitamin C 3000mg (2 capsules) twice a day		X	X	X	X	X	X	X	X	X	X								
Vitamin D 3000IU (2 capsules) twice a day		X	X	X	X	X	X	X	X	X	X								
Zinc 50mg (2 capsules) twice a day		X	X	X	X	X	X	X	X	X	X								
Vitamin C 1500mg (1 capsule) twice a day												X	X	X	X	X			
Vitamin D 1500IU (1 capsule) twice a day												X	X	X	X	X			
Zinc 25mg (1 capsule) twice a day												X	X	X	X	X			
Ask about AE and SAE				X				X			X				X		X	X	X
Vitals in-clinic f																	X	X	X
Physical exam																	X	X	X
EKG in-clinic																	X	X	X
Swabs for RT-PCR				X		X		X							X		X		X
Bloodwork g																	X	X	X
Review list of prior and concomitant medications		X	X	X	X	X	X	X	X	X	X	X	X	X	X	X	X	X	X
SARS-CoV-2 Antibody test (optional, +4 days)																	X		
Blood Hydroxychloroquine level (optional)																	X		

- a. To include hydroxychloroquine 200mg tablets (#20), azithromycin 250mg tablets (#6), vitamin C 750mg capsules (#80), vitamin D 750IU capsules (#80), zinc 12.5mg capsules (#80)
- b. To include EKG (worn continuously), pulse oximeter, and thermometer
- c. If Subject is a woman of childbearing potential
- d. To remind them to collect swabs for RT-PCT, ask about AE/SAE, ask about symptoms, and answer any questions

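### The protocol gives two conflicting screening windows, and its primary endpoint runs from a diagnosis date that neither window limits, so variable untreated time enters the endpoint

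*Combined protocol and SAP*

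**What the plan says.** **Screening window.** Section 3 (Study Procedures) gives one window: "Screening, Day -3 to Day -1". Confirmation of diagnosis, randomisation and prescription are listed under it. Section 6 (Schedule of Events) gives another in its column heading: "Screening (Day -7 to Day 1". Nothing in the protocol says which prevails.

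**Endpoint clock.** The synopsis endpoint table has "Number of days from COVID-19 diagnosis to recovery via RT-PCR", and Section 2 (Trial Objectives) has "Number of Days Recovery from COVID-19 diagnosis to Recover via RT-PCR". Both start at diagnosis.

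**When diagnosis happens.** The synopsis, under Duration of Subject Participation, says "Subjects will be given the opportunity once diagnosis has been made via RT-PCR testing to participate" and "The diagnosis will be made by the Subject's evaluating physician or evaluation testing center". Section 3 has the diagnosis confirmed at screening, on PCR results, "rapid antigen testing results, or clinical presentation at screening as assessed by the Principal Investigator". The inclusion and exclusion criteria set no limit on time since diagnosis. Section 3 also labels Day 1 by reference to the positive test, which is a further possible anchor.

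**Dosing and swabs.** Study drug is shipped to the home after randomisation and started on Day 1. On-study swabs fall on Days 3, 5, 7 and 14 and at Months 1 and 3; there is none on Day 1.

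**A competing definition.** Section 15 (Statistical analysis) names a change from baseline to end as the primary outcome. That measure does not use the diagnosis date.

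**The concern.** A subject screened on Day -6 complies with the schedule and breaches Section 3. Site staff, monitors and programmers cannot follow both.

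The matter goes beyond tidiness because of the endpoint. Days before the first dose cannot be shortened by study drug, yet a clock that starts at diagnosis counts them. The more variable this lead-in is, the noisier the endpoint; the longer it is, the smaller a given benefit looks in proportion to the total. Some subjects will also turn negative before they take any drug, and without a Day 1 swab they cannot be told apart from subjects who cleared between Day 1 and Day 3.

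**Working it through.** **1. The plan's own figure.** Section 15 computes n = log(0.05)/log(0.995) = 597.647, used as 600. This reproduces. The screening window is not an input, so the stated sample size does not move.

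**2. Lag from screening to Day 1.** From the two window headings:

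| Counting | Section 3 | Schedule of Events |
|---|---|---|
| No Day 0 | 1 to 3 days | 0 to 7 days |
| With a Day 0 | 2 to 4 days | 0 to 8 days |

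The maximum differs by 4 days either way. These lags equal untreated time in the endpoint only if diagnosis falls on the screening day, which is an assumption. An earlier outside diagnosis adds to them without a stated limit.

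**3. Share of the endpoint that is untreated, at the window limit.** With no Day 0, a first negative swab on Day d gives an endpoint of lag + (d - 1) days.

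| First negative swab | Lag 3 (Section 3 limit) | Lag 7 (schedule limit) |
|---|---|---|
| Day 3 | 3/5 = 60% | 7/9 = 78% |
| Day 7 | 3/9 = 33% | 7/13 = 54% |
| Day 14 | 3/16 = 19% | 7/20 = 35% |

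**4. Subjects negative before the first dose.** The protocol gives no clearance curve. Assume exponential clearance from the screening day with median m, so the proportion negative after t days is 1 - 2^(-t/m). With m = 8, the values for t = 0 to 7 are 0, 0.083, 0.159, 0.229, 0.293, 0.352, 0.405 and 0.455.

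- Even spread over 1 to 3 days: (0.083 + 0.159 + 0.229)/3 = 0.157, about 16%.
- Even spread over 0 to 7 days: 1.976/8 = 0.247, about 25%.
- Every subject at the limit: 23% at 3 days, 45% at 7 days.

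The same calculation for other assumed medians, with no Day 0:

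| Median (days) | Even spread, Section 3 vs schedule | All at the limit, Section 3 vs schedule |
|---|---|---|
| 6 | 20% vs 31% | 29% vs 55% |
| 8 | 16% vs 25% | 23% vs 45% |
| 10 | 13% vs 21% | 19% vs 38% |
| 12 | 11% vs 18% | 16% vs 33% |

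With a Day 0 and m = 8, the even-spread figures are 23% (lags 2 to 4) and 28% (lags 0 to 8), so the gap narrows.

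**5. Noise, as an illustration only.** An evenly spread lag has SD 0.82 days under Section 3 and 2.29 under the schedule (no Day 0). Treat it as independent of clearance time from Day 1, so total SD = sqrt(SD² + lag SD²). Assume 300 per arm, two-sided 0.05 and a 1-day difference; the allocation, SDs and effect are not in the protocol.

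| Assumed SD from Day 1 | Total SD, Section 3 vs schedule | Power, Section 3 vs schedule |
|---|---|---|
| 3 | 3.11 vs 3.77 | 98% vs 90% |
| 5 | 5.07 vs 5.50 | 68% vs 61% |
| 7 | 7.05 vs 7.37 | 41% vs 38% |

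**The case against.** The strongest reply is that the window does not control the quantity at issue. It bounds screening to Day 1, whereas the endpoint starts at a diagnosis that may come earlier. That stands. A reader might infer that the choice of window fixes how much untreated time the endpoint holds; the protocol does not support this, since untreated time is uncapped under both windows and reconciling them would not cap it. What follows is that the clock's origin matters more than the window.

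Second, randomisation balances lead-in time in expectation. This also stands. A reader might infer a biased treatment comparison; nothing in the protocol supports that. The comparison with an existing database of de-identified subjects, mentioned in Section 15, is not protected in this way.

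Third, exclusion criterion 4 removes subjects who test negative at screening. It is a partial safeguard: it misses those who convert between screening and Day 1, and those entered on clinical presentation without a test.

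Fourth, Section 15 names a post-minus-pre change as the primary outcome, to which the argument does not apply in this form. That is a separate inconsistency, and it does not remove the diagnosis-based endpoint from the synopsis and Section 2.

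**Conclusion.** The contradiction between the two windows is certain and needs no assumption. That the diagnosis-based endpoint contains variable, uncapped pre-treatment time also follows directly from the text. The consequence is added noise and a diluted proportional effect.

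The size is conditional. The limits of 3 versus 7 days require diagnosis on the screening day and no Day 0. The 16% versus 25% further requires exponential clearance with a median of 8 days and evenly spread lags; over medians of 6 to 12 days the range runs from 20% versus 31% down to 11% versus 18%. It is tempting to read 23% versus 45% as the typical effect of the longer window, but that places every subject at the window limit, and nothing in the protocol says so.

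The protocol does not show which window was intended. The point is minor, but worth correcting because the remedy is cheap.

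**What to change.** 1. State one screening window in both Section 3 and the Schedule of Events, ending before the first dose.
2. Start the primary endpoint clock at one defined origin in the synopsis and Section 2. Day 1 (first dose) removes lead-in time entirely. Randomisation is the alternative if the sponsor accepts that shipping time stays in; the two are not equivalent.
3. Record the diagnosis date as a baseline variable.
4. Align the result with the post-minus-pre primary outcome in Section 15.

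**Cost.** No added visits or subjects. The primary endpoint wording changes in two places, and the reported days to recovery become shorter.

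**What it does not do.** A new origin takes lead-in time out of the endpoint but does not identify subjects who cleared virus before Day 1. They stay in the trial, and the Day 3 swab is still the first to show them.

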## 15. Statistical analysis

The treated patients in this study will be compared to the placebo group. Measurements will include PCR test results, presence or absence of symptoms, and symptom severity. PCR results will be compared between the groups as positive or negative

In this study, the meaningful threshold will be calculated as mean change in clinical symptoms as recorded in the diary, from Day 1 through week 12. Each category in the diary will be assigned a number, 0 for None, 1 for Mild, 2 for Moderate and 3 for severe. Each category will be analyzed independently and they will be analyzed as a group. Ultimately, efficacy will be determined based upon reduction and/or progression of symptomatic days, reduction of symptom severity, as well as analysis of the subject's RT-PCR testing per protocol. These data will be compared to an existing database of de-identified Subject data.

The change of these measurements from the end to the baseline (post-pre) will be used as the primary outcome, for example,  $\mu_e = \mu_{e1} - \mu_{e0}$ , where  $\mu_{e1}$  and  $\mu_{e0}$  are the outcome of Subjects from the treatment group at the end and at baseline, respectively.

Categorical variables will be summarized by presenting the number (n) and percent (%) of subjects in each category. All Statistical tests for the analysis will be performed using the  $p < 0.05$  level of significance. All confidence intervals will be one-sided

Sample size was calculated as follows:

$$n = \frac{\log \beta}{\log \rho}$$

Where  $\beta = \text{the probability of a Type II error}$

$\rho = \text{the proportion of the population NOT affected}$

The proportion of the population affected by COVID-19 is 0.005 percent, thus 0.995 percent aren't affected

The probability of a type II error is 0.05

Thus:

$$n = \frac{\log 0.050}{\log 0.995}$$

$$n = 597.647$$

A sample size of 600 will be used

Additional details can be found in the Statistical Analysis Plan that will be developed prior to database lock.

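### No step secures a symptom score before the first dose, so the baseline of Section 15's change-from-baseline outcome can already reflect the randomised drugs

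*Combined protocol and SAP*

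**What the plan says.** **The outcome.** Section 15 scores each diary category from 0 (none) to 3 (severe), takes mean symptom change from Day 1 to week 12, and states: "The change of these measurements from the end to the baseline (post-pre) will be used as the primary outcome". It does not say which entry is the baseline, or that it must precede treatment.

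**Section 3, screening.** "Subject will be provided a daily diary for recording symptoms". No entry is requested at that point.

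**Section 3, Day 1.** The steps are, in order: a video call, a pregnancy test where applicable, vital signs (EKG, oxygen saturation, temperature) and the regimen. Within the call, under the item on using the home equipment, comes: "Subject will take baseline measurements at this time and record it in the diary". Instruction on the diary is a separate item. There is no step to complete the symptom diary.

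**Section 3, Day 2.** The first request for symptom entries appears: "Subject will complete AM and PM diaries".

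**Section 6, Schedule of Events.** The row "Subject will complete AM/PM diary" is marked from Day 1 to Day 30 and is empty at Screening. No footnote orders the entry relative to the dose.

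**Dose timing.** Section 3 says: "Drugs shall be taken first thing in the morning as soon as the patient has eaten". The only explicit pre-dose rule is in the synopsis and covers the home EKG, which is "to be read by a board-certified cardiologist prior to dosing".

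**The concern.** A change score compares the arms fairly only if the baseline was measured before treatment could affect it. Followed as written, Section 3 gives a first symptom score on Day 2, when the active arm has already had a day of both randomised drugs. The Schedule gives a Day 1 pair of entries. The PM entry follows the morning dose, and nothing prevents the AM entry from following it too.

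The drugs could plausibly move such a score. Section 13.1 lists nausea, vomiting, diarrhoea, abdominal pain and headache for both hydroxychloroquine and azithromycin. Section 1 names headache and GI symptoms among the symptoms of COVID-19. Section 13.1 also lists fever, cough and anosmia for azithromycin, and Section 3 uses these three as examples of diagnostic symptoms. Vitamins and zinc go to both arms, so only the two randomised drugs can separate the baselines.

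A pre-dose score that was never collected cannot be recovered later, including by the Statistical Analysis Plan that Section 15 defers until before database lock.

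**Working it through.** **1. What precedes the first symptom entry**

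| Source | First symptom entry | Randomised treatment taken before it |
|---|---|---|
| Section 3 | Day 2 AM | At least two hydroxychloroquine/placebo doses and the Day 1 azithromycin/placebo dose |
| Schedule of Events | Day 1 AM/PM | AM entry: none, or the first morning dose (order not fixed). PM entry: the morning dose |
| Section 15 | Not identified; change runs from Day 1 | Not stated |

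**2. How a shifted baseline enters the result**

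Let B be the true pre-dose mean in both arms, E1 and E0 the end means (active, placebo), and b the shift that the drugs cause in the active arm's recorded baseline.

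- Active change: E1 − (B + b). Placebo change: E0 − B.
- Difference: (E1 − E0) − b.

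With no true difference at the end, the expected difference is −b. If early side effects raise the score (b > 0), the active arm appears to improve more. If the drugs relieve symptoms before the first entry (b < 0), part of their benefit is subtracted. Adjusting for the recorded baseline with slope γ changes the bias from −b to −γb. It does not remove it, because the covariate is itself affected by treatment.

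**3. Does the plan supply a size?**

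The plan's own figure reproduces: log 0.050 / log 0.995 = 597.647, rounded up to 600. That formula contains no baseline, effect size or SD. The documents also give no list of scored diary items, early side-effect rate or allocation ratio. So b and its effect on the test cannot be derived.

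**4. Illustration on assumed values only**

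Assumptions: 1:1 allocation (600 / 2 = 300 per arm), no true effect at the end, SD of the change in the group score 3 or 4, and b gone by the end.

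- SE = SD × √(2/300). SD 3: 0.245. SD 4: 0.327.
- z = b / SE.
- Two-sided rejection rate = P(Z > 1.96 − z) + P(Z < −1.96 − z).

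| Assumed b | z, SD 3 | Rejection, SD 3 | z, SD 4 | Rejection, SD 4 |
|---|---|---|---|---|
| 0.2 | 0.816 | 13% | 0.612 | 9% |
| 0.4 | 1.633 | 37% | 1.225 | 23% |
| 0.6 | 2.449 | 69% | 1.837 | 45% |

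Section 15 sets p < 0.05 without stating sidedness and makes its intervals one-sided. At one-sided 0.05 with SD 3, the chance of falsely favouring active is about 20%, 50% and 79%. Only the ratio b/SD matters: b = 0.2 with SD 1 gives the same 69% as b = 0.6 with SD 3. If b = 0, the rate is the nominal 5%. If b is negative, the two-sided rates are the same but the false result favours placebo.

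**The case against.** The strongest reply is that a pre-dose Day 1 baseline is clearly intended. Section 15 speaks of Day 1 and of post minus pre, and the Schedule marks Day 1. The Day 1 steps in Section 3 put a baseline entry in the diary ahead of the regimen, and the synopsis makes dosing wait for a read EKG. On this view the missing Day 1 diary line is a clerical omission. Much of this stands: a subject following the Schedule could well complete the AM diary before dosing, and then there is no bias. But the Day 1 baseline step concerns equipment readings, and those devices do not measure nausea or headache. The EKG rule does not extend to symptoms. The intention is visible, but no procedure delivers it.

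Second, the change score is not the only primary endpoint. Section 2 and the synopsis name days from diagnosis to recovery by RT-PCR, and Section 2 treats symptom response as secondary. The measurements in Section 15 also include PCR results. This objection stands and limits the point to symptom change. It does not dispose of it: the synopsis also places symptomatic days and severity under the primary objective, and Section 15 bases efficacy partly on them.

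Third, the diary's scored items are not shown, and Appendix 3 says adverse events are asked about by phone and in the diary. That the scored items overlap with side effects is plausible but not established. This stands.

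A reader might infer that the trial is set to show a spurious benefit, with a false-positive rate as high as 69%. The documents do not support that. The shifts and SDs are assumed, the direction is open, and the shift is zero if the Day 1 AM entry is made before dosing.

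**Conclusion.** The point holds in a limited form. Section 3 and the Schedule disagree on the day of the first symptom diary, and neither requires it before the first dose. Section 15's symptom-change outcome therefore has no assured pre-treatment baseline, and the between-arm comparison can be biased either way. Days to RT-PCR recovery needs no symptom baseline and is untouched.

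The size is unknown. The range of 13% to 69% shows only how sensitive the test would be to shifts of 0.2 to 0.6 points, given SD 3, 300 per arm, no true effect, and a shift that has gone by the end. It does not estimate this trial's error rate. The case for acting rests on two facts: the missing score cannot be reconstructed afterwards, and collecting it costs almost nothing.

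A minor related point concerns vital signs and oxygen saturation, which are secondary endpoints. For the screening-record values of vital signs, EKG and oxygen saturation, Section 3 says: "These values will be used to compare to values obtained throughout the study". It then also takes a home-device baseline on Day 1. Both can be kept, but the plan does not say which one is the baseline for analysis.

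**What to change.** - **Section 3, Day 1:** before the regimen, add a step in which the subject completes every symptom diary item before the first dose, with the time recorded.
- **Section 6:** make the Schedule match, with a footnote that the Day 1 baseline entry is pre-dose.
- **Section 15 and the Statistical Analysis Plan:** define the symptom baseline as that pre-dose entry and treat later entries as post-baseline.
- **Minor:** state which reading is the baseline for oxygen saturation and vital signs. The Day 1 pre-dose home reading is preferable wherever the same device supplies the later values.

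The cost is a few lines of text. The diary is already handed out at screening and the Day 1 video call already exists, so no visit or equipment is added and no dose or clinical rule changes.
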